There is emerging evidence that the gut milieu plays an important role in the progression of complications of cirrhosis [1–3]. Studies have found dysbiosis in the gut microbiota in patients with cirrhosis that has the potential to influence complications such as hepatic encephalopathy [1,2]. The gut milieu in cirrhosis involves the interaction between the microbiota and secreted factors, such as bile acids (BAs) that can also modulate the gut barrier [4]. The gut microbiota is known to convert 7a-dehydroxylate primary BAs and chenodeoxycholic acid (CDCA) and cholic acid (CA) into the secondary bile acids lithocholic acid (LCA) and deoxycholic acid (DCA), respectively [5]. Cirrhotic patients have been shown to have a lower proportion of secondary BAs in their bile but the mechanism for this is not clear [6]. Since BAs have important downstream pathophysiologic effects, a better understanding of the interaction between the intestinal microbiome and BAs is important to gain insight into the pathophysiology of cirrhosis [7,8]. In Genta Kakiyama study[9], the median abundances of taxa are shown with significantly higher Enterobacteriaceae and Veillonellaceae and lower autochthonous bacteria (Blautia, Ruminococcaceae, Lachnospiraceae) in cirrhotics, especially advanced cirrhotics compared to healthy controls. The total bile acid was 206.5 µg/100 mg dry stool in healthy control, and 39.0 in advanced cirrhosis. The secondary BAs were present in a significantly lower percentage of cirrhotics. The ratios of all secondary to primary BAs, and specifically of DCA/CA and LCA/CDCA, were also the lowest in advanced cirrhosis. Cirrhosis dysbiosis ratio (CDR), the ratio of autochthonous/good bacteria (e.g. Lachnospiraceae, Ruminococcaceae and Clostridiales) to non-autochthonous/ pathogenic bacteria (e.g. Enterobacteriaceae and Streptococcaceae), is significantly higher in controls and patients with compensated cirrhosis than patients with decompensated cirrhosis. Increasing CDR could lead to develop the hepatic encephalopathy[10]. Bile acids are also the endogenous ligands of Farnesoid X receptor (FXR), Takeda G protein receptor 5 (TGR5) and Sphingosine-1-phosphate receptor 2 (S1PR2). These receptors are placed at the interface of the host immune system with the intestinal microbiota and are highly represented in cells of innate immunity such as intestinal and liver macrophages, dendritic cells and natural killer T cells[11]. In human study, ursodeoxycholic

acid (UDCA) could enhance the bile synthesis by CYP7A1 altering the gut microbiota population. UDCA also has other beneficial effects, such as anticholestatic, antifibrotic, antiproliferative, and anti-inflammatory [12-14].

In retrospective studies, statins appear to be safe in patients with compensated cirrhosis, and evidence suggests that they may significantly reduce fibrosis (HR:0.56, p<0.0001)[15]. Preclinical data from studies performed on in vitro and in vivo animal models shed light on favorable effects of statins on endothelial function, angiogenesis, PHTN, and fibrosis. Suggested mechanisms involve regulation of KLF2, eNOS, thrombomodulin, and C-natriuretic peptide. Animal studies evidence suggests that the administration of fluvastatin, lovastatin, and simvastatin to primary rat hepatocytes and human hepatoma cell line inhibits the paracrine activation of HSCs [16], reduces HSC turnover and activity [17,18]. Moreover, Nature (2020) reported statin therapy is associated with lower prevalence of gut microbiota dysbiosis. [19]

The combination of ursodeoxycholic acid and statins is safe in human experiments, and the combination of the two has also proved to have a synergistic effect on the reduction of bile cholesterol levels [20], but there is no research on improving fibrosis makers or improving intestinal flora.

The goal of the current study was to evaluate our hypothesis model of pathogenesis of chronic inflammation of liver cirrhosis. We hypothesized that an adverse microbiome would exacerbate the histopathological severity of liver induced by CCL4 in a germ-free mice model. We transplanted these mice with human fecal samples from healthy controls, or liver cirrhosis treated with statin, or UDCA. The clinical trial mainly explores whether single statin or combined ursodeoxycholic acid can reduce liver fibrosis indicators, inflammatory cytokines and intestinal flora imbalance in patients with liver cirrhosis who have been cured of chronic hepatitis C or non-viral load hepatitis B.

Patients and assessments- Study design

We expect to enroll 120 stable patients who have achieved sustained viral response (SVR) (ie, viral eradication) after hepatitis C treatment for 6 months, or non-viral load hepatitis B for 6 months, who have been diagnosed with primary cirrhosis (FIB-4 \geq 3.25) and met the Baveno VII criteria (liver stiffness measurement [LSM] \geq 25 kPa) and exclude it (LSM <15 kPa and platelet count [PLT] \geq 150 \times 10⁹/L) were used. Grey zones were classified into two groups: (high – LSM between 20–25 kPa and PLT <150 \times 10⁹/L, or LSM between 15–20 kPa and PLT <110 \times 10⁹/L, or low – defined as the remaining patients within the grey zone) [27]. **Exclusion conditions:** already taking statins, diabetes, liver cancer, alcoholic liver, moderate to severe fatty liver, liver decompensation (jaundice, ascites, esophagogastric varices, history of hepatic coma), chronic kidney disease, antibiotic use within three months and gastric ulcer medication(such as PPIs). Randomly divided into three groups: **Group 1:** control group (n =

30), Group 2: treatment group (ursodeoxy Cholic acid (UDCA) (10mg/kg/day) (n = 30), Group 3: treatment group (simvastatin 40mg) (n = 30), Group 4: treatment group (simvastatin 40mg/day + ursodeoxy Cholic acid (UDCA) (10mg/kg/day) (n = 30). Fecal bile acid content and fecal flora, skin bile acid profile, cytokine markers, biochemical fibrosis biomarker were collected at the test base point and six months after treatment. In addition, patients who achieved virus eradication without liver cirrhosis (FIB-4 < 1.45, n=30) collected the content of fecal bile acid, fecal flora, skin bile acid, and inflammatory cytokines were collected at the test base point index, biochemical fibrosis biomarkers. Analysis of flora: 16S ribosomal RNA gene sequence analysis from the patient's fecal tube. Analysis of total fecal bile acid: LC-MS/MS system analysis. Skin bile acid profile:Desorption-Electrospray Ionization Mass Spectrometry (TD-ESI/MS).

Block randomization

Patients (n=120) were distributed on one block with 8 numbers and each group contained two numbers (1, 2, 3, 4). The admitted patients who were eligible for inclusion were given numbers in the order; number 1 was allocated to (control group) as the study group, patients who carried number 2 was allocated to (UDCA group),patients who carried number 3 was allocated to (simvastatin group), and number 4 was allocated to (simvastatin plus UDCA group). Therefore, the control and three interventional groups were randomized into 1:1:1:1.

Stool sample preparation and microbiota analysis

Bile juice and biliary stents samples will be collected in separate sterile containers containing 2mL of RNA later and will be stored at room temperature. The samples will be transferred to the laboratory within 12 h, stored at 4°C, and used for extracting DNA within few weeks. Preliminary experiments will confirm that the bacterial composition data does not change in four weeks under the storage conditions used. Genomic DNA will be isolated from stool samples using the CTAB/SDS methods (Novogene Laboratories) following the manufacturer's protocol. All microbial community DNA samples will be analyzed for V4 variable region of bacterial 16S ribosomal RNA gene using PCR primers 515F and 806R. The PCR products will be separated by 2% agarose gel electrophoresis. Samples with bright main strip between 400-450bp will be chosen for further experiments. PCR product will be mixed in equidensity ratios. Then, mixture PCR products will be purified with Qiagen Gel Extraction Kit (Qiagen, Germany). Sequencing libraries will be generated using TruSeq DNA PCR-Free sample Preparation Kit (Illumina, USA) following manufacturer's recommendations and index codes will be added. The library quality will be assessed on the Qubit® 2.0 Fluorometer (Thermo Scientific) and Agilent Bioanalyzer 2100 system. At last, the library will be sequenced on an IlluminaHiSeq2500 platform and 250 bp paired-end reads will be generated.

Fecal bile acid profile [20].

A stool sample was obtained and dried to obtain a lyophilized extract. To lyophilized faecal samples weighing 1 g, 80% methanol was added. All samples were sonicated for 30 min, refluxed for two hours, and then cooled and filtered. The residue was re-suspended in chloroform/methanol (1:1, v/v), refluxed for one hour, and filtered. The combined extracts were taken to dryness, and re-suspended in 10 ml methanol (MeOH). An aliquot of 1 ml was added with 2 μ l of 1 mg/ml nordeoxycholic acid, and was diluted in 10 ml deionized water and deposited on a 300 mg HLB Oasis column, washed with 10 volumes deionized, 1 volume cyclohexane, and the BAs were then eluted with 5 ml MeOH and were taken to dryness and resuspended in 250 μ l MeOH. Four microliters were injected on liquid chromatography coupled with tandem mass spectrometry (LC-MS/MS) as previously described.

Skin bile acid profile [22]

TD-ESI source comprised of a direct probe (DP), thermal desorption unit, and electrospray ionization device. First, the direct probe (DP) was used for sampling analytes in solution or on solid surfaces. For liquid samples, a stainless steel inoculating loop serving as a probe (2 mm in diameter) was used to obtain approximately 2 μ L of sample solution for each analysis. For viscous solutions or solid samples, a straight fine needle (350 μ m in diameter) was used to either collect analytes of viscous solutions or sweep five times across solid surfaces to obtain analytes. Second, the function of the thermal desorption unit was to vaporize samples on the DP and introduce desorbed analytes into the ESI plume through a quartz tube with single taper (OD= 6 mm, ID= 4 mm, Length= 80 mm) so that effective sample ionization can take place. In addition, an opening in the thermal desorption unit was created when the direct probe was removed from the unit to sample analytes. The thermal desorption unit was sealed after the direct probe was placed back on the thermal desorption unit for analysis of sample analytes on the probe. Third, an electrospray ionization device was used for post-ionizing desorbed analytes. The high voltage and solvent flow rate required to generate an electrospray plume were 5 kV and 2.5 μ L/min, respectively. The ESI solution was a methanol and water mixture (1:1, v/v) containing 0.1% acetic acid, and was delivered through a fused-silica spray capillary (ID= 100 μ m, OD= 375 μ m, Polymicro, Phoenix, AZ) into the mass inlet of the mass spectrometer. The TD-ESI source was attached to a triple quadruple mass spectrometer (Agilent 6410) to detect the analyte ions. To obtain a stable solvent and analyte ion signal, the electrospray capillary was aligned to the MS inlet and the distance from the exit of the TD tube to the electrospray capillary (d_1) was kept at 8 mm, while the distance from the MS inlet to the electrospray capillary (d_2) was 5 mm. The temperature in the thermal desorption unit was set at 250 °C and was measured by a thermistor installed in the source. The flow rate of the nitrogen gas used to deliver desorbed analytes into the ESI plume was 0.8 L/min.

Primary end point: Fibrosis biomarker [23]

Molecular markers of fibrogenesis including TGF- β 1, and Type IV collagen. Hyaluronic Acid in the serum blood test, and clinical laboratory FIB-4 Index.

Secondary end points: 1. Cirrhosis dysbiosis ratio (CDR), the ratio of autochthonous good bacteria (e.g. Lachnospiraceae, Ruminococcaceae and Clostridiales) to non-autochthonous/ pathogenic bacteria (e.g. Enterobacteriaceae and Streptococcaceae). 2. Total stool bile acid, Secondary and primary bile acid ratio. 3. Serum inflammation peptides (IL-6, IL-8, IL-10, and TNF-a)

Sample size : Till now, there was no prospective data to support the evaluation the sample size of study in the liver fibrosis deminition after the administrations of stain and UDCA. Prior data [24]may indicate the effect of 40 mg simvastatin versus placebo on hepatic portal pressure was studied over a period of 3 months. A significant decrease in HVPG (-15%) was noted in the experimental group versus no change in the placebo group. The study included 24 cases in each study arm. Therefore, we plan to enroll 30 participants in each arm.

Safety

Initial dose of study drug is 20 mg which can be increased to 40 mg after 4 weeks if the participant does not develop side effects. Creatine kinase and standard biochemistry including liver enzymes are measured for safety reasons after 2 weeks, to rule out myositis and liver damage. Side effects and events are consecutively registered throughout the trial. Safety of statins in chronic liver disease has been assessed in only a few clinical trials, but reviews of observational studies report high safety and low risk of adverse events, even significantly lower the all-cause mortality [25,26]

Statistical analysis:

Risks are reported as IRRs along with their 95% confidence intervals and P values. For subgroup analyses according to sample characteristics, P values for interaction also are assessed. The cumulative proportion of patients developing liver fibrosis events during follow-up is estimated by life table methods and log-rank tests were reported. P values are 2-sided, and values of .05 or less are considered statistically significant. All statistical analyses are performed using SAS version 9.1 (SAS Institute Inc).

Limitation 1:

If post treated human feces contain the trace level of drug, the hypothesis that it is caused by microorganisms alone does not hold. We will check the post treated human feces by the TD-ESI (LTQ)for simvastatin (Formula: $C_{25}H_{38}O_5$, Exact mass: 418.57 Da),and Ursodeoxycholic acid (UDCA)(Formula : $C_{24}H_{40}O_4$. Exact mass : 392.29 Da). The pre-test was performed by TD-ESI (LTQ) as followed figures.

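### The exclusion list bars prior users of statins but not of UDCA, the other randomised drug, so prior UDCA users can enter all four arms and weaken the UDCA contrasts

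*Protocol*

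**What the plan says.** All of the eligibility text is in the protocol, under Patients and assessments – Study design. The exclusion list begins "already taking statins, diabetes, liver cancer, alcoholic liver, moderate to severe fatty liver", goes on to hepatic decompensation, and ends with "chronic kidney disease, antibiotic use within three months and gastric ulcer medication(such as PPIs". Three kinds of medication are therefore named: statins, recent antibiotics and gastric ulcer drugs. UDCA is not among them. No other section of the protocol gives a rule on prior or concomitant UDCA.

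The same section makes UDCA a randomised drug in two of the four arms: "Group 2: treatment group (ursodeoxy Cholic acid (UDCA) (10mg/kg/day) (n = 30") and "Group 4: treatment group (simvastatin 40mg/day + ursodeoxy Cholic acid (UDCA) (10mg/kg/day) (n = 30"). Groups 1 (control) and 3 (simvastatin) are the arms without UDCA. Under Block randomization the allocation is 1:1:1:1.

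On timing, "biochemical fibrosis biomarker were collected at the test base point and six months after treatment", together with stool bile acids, flora and cytokines. The primary end point is a set of fibrosis markers. The secondary end points are the cirrhosis dysbiosis ratio, "Total stool bile acid, Secondary and primary bile acid ratio", and serum inflammation peptides.

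The introduction says that UDCA "could enhance the bile synthesis by CYP7A1 altering the gut microbiota population", and also credits it with antifibrotic and anti-inflammatory effects.

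**The concern.** The list already accepts that prior use of a study drug spoils the comparison, but it applies this to only one of the two study drugs. On the protocol's own account, UDCA acts on every family of end points: fibrosis markers, flora, bile acids and inflammation. For stool bile acids the link is direct, since UDCA is itself a bile acid and can form part of the measured quantity at baseline and at six months.

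At stake is what the UDCA contrasts estimate. With prior users admitted, they no longer compare starting UDCA with not taking it, and the baseline for some patients is not a UDCA-free one. Eligibility is fixed in the protocol, so this is not a detail that would normally be left to a statistical analysis plan.

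**Working it through.** **Reading the list against the arms.** A prior UDCA user who meets the other criteria can be allocated in three ways that matter:

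| Allocation | Behaviour | Consequence |
|---|---|---|
| Group 1 or 3 | continues UDCA | exposed in an arm meant to be UDCA-free |
| Group 1 or 3 | stops UDCA | change from baseline contains a withdrawal response |
| Group 2 or 4 | takes allocated UDCA | no UDCA-free baseline |

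The protocol does not say whether the first or the second row applies.

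**Effect on the contrast.** Let Δ be the true effect of starting UDCA and q the share of prior users, equal across arms in expectation because of randomisation. Assume that prior users already show the full effect at baseline.

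- *Continuing, six-month values.* UDCA arm: Δ. UDCA-free arm: qΔ. Difference: (1 − q)Δ.
- *Continuing, change from baseline.* UDCA arm: (1 − q)Δ, because prior users have nothing further to gain. UDCA-free arm: 0. Difference: (1 − q)Δ again.
- *Stopping, change from baseline.* Let w be the mean change in patients who stop. UDCA arm: (1 − q)Δ. UDCA-free arm: qw. Difference: (1 − q)Δ − qw. With w = 0 this is the diluted value. With full reversal, w = −Δ, it is Δ. With a rebound beyond that it exceeds Δ. The documents give no value for w, so the net direction is unknown.

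**Which contrasts are affected.** The factor (1 − q) applies fully to Group 2 v 1 and Group 4 v 3. In Group 4 v 1 it applies only to the UDCA component. Group 3 v 1 compares simvastatin with control, with prior UDCA use balanced in expectation, so it is not diluted by this mechanism.

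**Illustrative size, continuation case only.** Inputs from the protocol are 30 per arm (Sample size) and two-sided 0.05 (Statistical analysis). The total agrees: 4 × 30 = 120. The Sample size section gives no power, SD or effect for the fibrosis markers, so there is no planned power to reproduce. The starting point here is an assumption: 80% power with a two-sample t-test at 30 v 30, which corresponds to 0.736 SD. The share q is also an assumption.

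| q | prior users expected per arm (30q) | effect left, 0.736 × (1 − q) | power at 30 v 30 |
|---|---|---|---|
| 0% | 0 | 0.736 SD | 80.0% |
| 1% | 0.3 | 0.728 SD | 79.2% |
| 5% | 1.5 | 0.699 SD | 75.9% |
| 10% | 3 | 0.662 SD | 71.3% |
| 20% | 6 | 0.588 SD | 61.1% |
| 30% | 9 | 0.515 SD | 50.1% |

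By the normal approximation, the number per arm that restores 80% is 30/(1 − q)², rounded up. This gives 34, 38, 47 and 62 at q = 5%, 10%, 20% and 30%.

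**Reference group.** The comparison group of "patients who achieved virus eradication without liver cirrhosis (FIB-4 < 1.45, n=30") has the same stool and serum measurements at baseline, and no UDCA rule is stated for it either.

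**The case against.** The strongest case against has four parts.

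- *Frequency.* Nothing in the protocol suggests that these stable patients, with virus eradicated or suppressed, often take UDCA. The drug is described as anticholestatic, and the exclusion of jaundice may remove some likely users. This stands: q may be near zero, and then almost nothing changes.
- *Baseline power.* The 80% is not a protocol figure. This also stands, so the table cannot be read as the loss of a planned property.
- *Direction.* A reader might infer that the omission necessarily biases the UDCA effect toward no difference, or that it undermines the whole trial. The documents support neither. Dilution requires that prior users in Groups 1 and 3 continue UDCA, which the protocol neither permits nor forbids; if they stop, the direction is open. The simvastatin v control comparison is not diluted.
- *Existing safeguards.* Stool bile acids are measured at baseline, and Limitation 1 plans to test post-treatment faeces for UDCA. These may reveal some exposure. But the faecal test is there for the mouse transplant work, is described for post-treatment samples, and keeps no prior user out.

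It can also be argued that the protocol is merely silent. Yet the list is specific about medication and names the other randomised drug. Followed as written, it admits prior UDCA users, and randomisation balances that use without restoring the contrast.

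**Conclusion.** The point holds in limited form. The exclusion list treats the two randomised drugs differently, and no other text in the protocol closes the gap. Prior UDCA users can therefore enter all four arms. If they continue in Groups 1 and 3, they dilute Group 2 v 1 and Group 4 v 3. If they stop, they distort the change from baseline in those arms in an unknown direction. In Groups 2 and 4 they lack a UDCA-free baseline for fibrosis markers, flora and stool bile acids.

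The flaw in the rule is certain; its size is not. In the illustration it runs from negligible (79% power at 1%) to serious (50% at 30%). That range rests on an assumed share, an assumed 80% starting power, an unchanged SD, and continued use by all prior users. Because the flaw is cheap to correct and the protocol has nothing to keep the share small, it should be corrected.

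**What to change.** Apply one eligibility rule to both randomised drugs: extend the first exclusion so that it covers patients already taking UDCA as well as those already taking statins. State whether the same rule holds for the non-cirrhotic reference group.

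For anyone already enrolled, record UDCA use at baseline and add a sensitivity analysis of the UDCA contrasts without prior users.

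The cost is one phrase in the list, one baseline item and one extra analysis. The downside is that a few otherwise eligible patients are screened out; if UDCA use is rare here, that loss is close to nil. No washout period or stopping rule is proposed, as these are clinical matters for the sponsor.

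### The fibrosis markers are measured at baseline and at six months, but the stated analysis uses no baseline value, so precision is lost with 30 per arm; because FIB-4 is also an entry threshold, a fall within one arm cannot be read as a treatment effect

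*Protocol*

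**What the plan says.** **Measurement times.** The Protocol, under Patients and assessments - Study design, lists the measures taken in the four randomised groups, the fibrosis markers last, and says that they "were collected at the test base point and six months after treatment". Every patient is therefore due a baseline and a six-month value of each fibrosis marker.

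**Entry.** The same section enrols patients "who have been diagnosed with primary cirrhosis", defined by FIB-4 of at least 3.25, together with liver-stiffness and platelet criteria.

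**Primary end point.** The section Primary end point: Fibrosis biomarker reads "Molecular markers of fibrogenesis including TGF- β 1, and Type IV collagen", followed by "Hyaluronic Acid in the serum blood test, and clinical laboratory FIB-4 Index". All four are continuous quantities, and FIB-4 is one of them.

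**Analysis.** The Statistical analysis section opens with "Risks are reported as IRRs along with their 95% confidence intervals and P values". It adds interaction P values for subgroups, and life-table and log-rank methods for liver fibrosis events. It mentions no baseline value, change score or covariate for any marker.

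**Comparator and size.** Block randomization describes 1:1:1:1 allocation with a concurrent control group. Sample size gives 30 per arm.

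**The concern.** There are two separate points.

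1. **Precision.** The baseline value of a continuous marker usually predicts its later value, so adjusting for it narrows the between-arm comparison without further patients. The protocol collects these values, and the analysis it states leaves them unused. This matters in a trial whose 30 per arm was set without a standard deviation or a power for any of its own end points.

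2. **Interpretation of FIB-4.** Patients selected because a reading lies above a cut-off tend to have a lower second reading, since some were selected on an upward fluctuation. FIB-4 is both the selecting quantity and a primary marker. The introduction states the aim as reducing fibrosis indicators, and no sentence says that a reduction must be judged against control. A fall within an active arm could then be reported as less fibrosis when selection produced it.

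**Working it through.** **Inputs from the protocol:** 30 per arm; two-sided 0.05; FIB-4 cut-off 3.25; two measurement times.

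**Assumed, because the protocol gives none:** the baseline to six-month correlation ρ, and the distribution and repeatability of FIB-4 in the source population.

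**Step 1: the plan's own figure.** The 30 per arm cannot be derived from what is stated. The section cites a study with 24 per arm and a 15% fall in portal pressure, with no SD, power or dropout. 24/(1 − 0.20) = 30 would fit, but no 20% dropout is stated. Taking 30 as given, the difference in six-month means detectable with 80% power is (1.960 + 0.842) × √(2/30) = 0.72 SD.

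**Step 2: precision.** Relative to unadjusted six-month values, the variance factor is 1 − ρ² for covariance analysis (ANCOVA) and 2(1 − ρ) for change scores. The ratio of the two is (1 + ρ)/2. The change-score formula assumes equal variance at both times.

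| ρ (assumed) | ANCOVA vs six-month values | 30 per arm acts like | Detectable difference | ANCOVA vs change scores |
|---|---|---|---|---|
| 0.5 | 0.75 (−25%) | 30/0.75 = 40 | 0.63 SD | 0.75 (−25%) |
| 0.7 | 0.51 (−49%) | 30/0.51 = 59 | 0.52 SD | 0.85 (−15%) |
| 0.8 | 0.36 (−64%) | 30/0.36 = 83 | 0.43 SD | 0.90 (−10%) |

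At ρ = 0.3 the gain over six-month values is only 9% (1 − 0.09 = 0.91), while change scores are worse than six-month values alone (factor 1.4).

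**Step 3: expected fall in FIB-4 if the qualifying reading is the baseline.** On the log scale, with SD s and test-retest correlation ρ in the source population, the expected change with no treatment effect is −(1 − ρ) × s × λ. Here λ = φ(a)/(1 − Φ(a)) and a = (ln 3.25 − ln median)/s. With a source median of 3.25, a = 0 and λ = 0.399/0.5 = 0.798. For s = 0.6:

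- ρ = 0.8: −0.2 × 0.6 × 0.798 = −0.096, a fall of 9.1%.
- ρ = 0.95: −0.05 × 0.6 × 0.798 = −0.024, a fall of 2.4%.

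Over source medians 1.8 to 4.0, s of 0.5 to 0.7 and ρ of 0.70 to 0.95, the fall runs from about 1% to 26%. A milder set (median 3 to 5, between-person log SD 0.35 to 0.50, within-person CV 10% to 25%) gives 0.6% to 12%. All are geometric means.

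**Step 4: which comparison is affected.** Null trials with 30 per arm were simulated (20,000 two-arm trials; median 3.25, s = 0.6):

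| Source ρ | Mean change | Significant within-arm fall | Between-arm false positives, six-month values / change | Correlation after selection |
|---|---|---|---|---|
| 0.7 | −13.3% | 40% | 5.0% / 4.9% | 0.51 |
| 0.8 | −9.1% | 28% | 4.6% / 4.9% | 0.63 |
| 0.9 | −4.7% | 16% | 5.4% / 4.8% | 0.78 |
| 0.95 | −2.4% | 10% | 5.0% / 4.8% | 0.88 |

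A within-arm fall should be declared in 2.5% of null trials. The between-arm rate stays near 5%.

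Selection also lowers the correlation among those enrolled. For FIB-4 the largest fall therefore goes with the smallest precision gain: at source ρ = 0.7 the gain is 0.508² = 26%.

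**The case against.** **Covariates are commonly left to the SAP, which is not at hand.** This is the strongest objection, and silence alone would not be a finding. But the protocol is not silent: it names an analysis that has no place for the paired marker values. A SAP would have to replace that analysis, not just add detail to it.

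**The precision gain is measured against analyses the protocol never names.** This is correct. Neither an unadjusted six-month comparison nor a change-score comparison is stated. The percentages show what the collected baseline is worth against the two obvious alternatives, at an assumed correlation.

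**A stronger reading is tempting on FIB-4.** A reader might infer that, because baseline is left out, FIB-4 will fall in every arm and the trial result will be biased. The documents do not support this, for four reasons:

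- The entry cut-off causes regression to the mean, not the missing covariate. Adding the covariate would leave the within-arm fall as it is.
- The fall depends on the qualifying reading serving as baseline. The protocol does not say whether it does.
- It affects randomised arms equally in expectation, so the contrast with control is unbiased (Step 4).
- No within-arm test is stated. Rate ratios and log-rank tests compare groups, and the sample-size argument cites an experimental against a placebo arm.

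**The size of the fall is uncertain.** This stands. The calculation selects on FIB-4 alone and ignores the liver-stiffness criterion, which may weaken the effect. No other primary marker is stated as an entry threshold.

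**Conclusion.** The point holds in two limited parts.

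- **Precision:** the stated analysis makes no use of baseline values collected for every primary marker. At an assumed correlation of 0.5 to 0.8, adjustment would make 30 per arm behave like 40 to 83 against six-month values alone, and like 33 (30/0.90) to 40 (30/0.75) against change scores. The direction is firm; the size rests on a correlation the protocol does not give.
- **Interpretation:** if the qualifying FIB-4 is also the baseline, some fall is expected in every arm without treatment effect. Under the assumptions tried it ranges from below 1% to about 26%, so no single figure should be quoted. The randomised comparison remains valid, but a before-after fall within an arm is not evidence of less fibrosis.

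This is a change that should be made. It is not a flaw that invalidates the design.

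**What to change.** In the Statistical analysis section:

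1. For each of TGF-β1, type IV collagen, hyaluronic acid and FIB-4, compare arms on the log six-month value with the log baseline value of the same marker as covariate (ANCOVA). Report each active arm against control with its confidence interval.
2. State that a reduction is concluded only from the between-arm contrast with control, never from a fall within an arm.

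The cost is analysis wording only. Both measurements are already planned, and no patients or procedures are added. A separate blood draw for baseline FIB-4 is not required, because the contrast in (1) is valid whichever reading serves as baseline, provided the same rule applies in all arms.

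### The block-randomisation paragraph states no random step and covers only 8 of 120 patients; even on its natural reading, the printed fixed block of 8 makes assignments partly predictable

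*Protocol*

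**What the plan says.** The protocol's section on block randomization gives the whole procedure in three sentences.

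- Structure: "Patients (n=120) were distributed on one block with 8 numbers and each group contained two numbers (1, 2, 3, 4").
- Assignment: "The admitted patients who were eligible for inclusion were given numbers in the order; number 1 was allocated to (control group"). Number 2 goes to UDCA and number 3 to simvastatin, and "number 4 was allocated to (simvastatin plus UDCA group").
- Conclusion: "Therefore, the control and three interventional groups were randomized into 1:1:1:1".

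Two other places bear on it. The study design section says "We expect to enroll 120 stable patients" and describes them as "Randomly divided into three groups", but then lists four groups of 30. The sample size section says "Therefore, we plan to enroll 30 participants in each arm".

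No random draw, permutation, generated list or list holder is described. The only placebo mentioned in the available text belongs to the earlier simvastatin study cited for the sample size.

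**The concern.** The conclusion of 1:1:1:1 randomisation does not follow from the steps before it. Numbering patients as they come and mapping the numbers to fixed arms involves no chance. A single block of eight also runs out after eight patients. Staff who follow the paragraph to the letter could allocate systematically and believe that they had randomised.

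Every between-arm comparison rests on this paragraph. If a recruiter can foresee or guess the next arm, a patient's enrolment can be timed or withheld according to expected course. Steering on recorded baseline measures could be adjusted for. Steering on features that nobody records could not.

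**Working it through.** **Inputs.** From the protocol: 120 patients, four arms, 30 per arm, a block of 8 with two places per arm. Assumed: the person guessing knows all earlier assignments and where each block starts.

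**The plan's own figure.** 120 / 8 = 15 blocks, and 15 × 2 = 30 per arm. The ratio and arm size are reproduced, but only if the block is repeated 15 times, which the text does not say. One block covers 8 patients and leaves 120 − 8 = 112 without a rule.

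**Procedures that fit the ratio.** Three procedures give 30 per arm, so the stated ratio does not show which was meant:

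| Procedure | Random step | Assignments guessable |
|---|---|---|
| Fresh random order in each of 15 blocks of 8 | yes, every block | 47.0% |
| One random 8-number order reused 15 times | first 8 only | (3.76 + 112) / 120 = 96.5% |
| Rotation 1-2-3-4 | none | 100% |

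The first is the natural reading. Nothing says that one order is reused, and a rotation would need only four numbers, not eight.

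**Predictability on the natural reading.** A block has 8! / (2!)⁴ = 2,520 possible orders. The best guess is always the arm with most places left. Averaged over all orders, the chance of a correct guess at places 1 to 8 is

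0.2500, 0.2857, 0.3333, 0.4000, 0.4429, 0.4762, 0.5714, 1.0000.

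The sum is 3.76 (exactly 1579/420) per block. So 3.76 / 8 = 47.0%, or 3.76 × 15 = 56.4 of 120, against 30 of 120 (25%) by chance.

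The eighth place is always certain. The seventh is certain when the last two places belong to the same arm, which has probability 1/7. That gives 1 + 1/7 = 1.143 per block, and 1.143 × 15 = 17.1 of 120 (14.3%).

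**What this could do to an endpoint.** This part is illustrative, because the protocol gives no figure for steering. Null trials were simulated with 30 per arm, outcome SD 1, and fresh blocks of 8. The expected outcome of the enrolled patient differed by 0.2 or 0.5 SD according to whether control was more or less likely than 1/4 to come next. Control was compared with one active arm by an unadjusted two-sided 5% t-test. With no steering the rejection rate was 4.96%, as it should be.

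| Share of opportunities steered | Spurious difference (SD) | Rejection under the null |
|---|---|---|
| All | 0.08 to 0.20 | 6.1% to 11.3% |
| Half | 0.04 to 0.10 | 5.3% to 6.6% |
| A quarter | 0.02 to 0.05 | 5.1% to 5.7% |

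Adjusting for a baseline value (assumed correlation 0.5 with the outcome) left the bias at 0.08 to 0.20 SD, with 6.4% to 13.2% rejection when every opportunity is steered. That run made the baseline independent of the steered feature, so adjustment could not help by construction. It represents steering on unrecorded features only.

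**The case against.** The strongest reply is that this is loose English for an ordinary method. The section is headed as block randomisation, the study design section says patients are randomly divided, eight places with two per arm is a standard block, and 15 of them give exactly the planned 30 per arm. Numbering by order may mean the order of a prepared list. Much of this stands. A reader might infer from the literal text that the trial used alternation and is not randomised. The documents do not support that: the intent is stated more than once, and rotation fits the eight numbers least well. The 96.5% and 100% figures therefore show what the wording permits, not what was probably done.

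It can also be said that fixed blocks are common, that 47.0% applies only to someone who tracks every assignment and block start, and that the endpoint effects rest wholly on assumed steering. This stands too. FIB-4 is both an eligibility measure and part of the primary endpoint, so steering on it would leave a record that an analysis could use.

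A reader might further infer that the trial has no blinding or concealment. The available text describes none, but some pages of the protocol were not available, so a statement there cannot be ruled out. Such a statement would weaken the predictability figure. It would not supply the missing random step or a rule for the other 112 patients.

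**Conclusion.** The point holds as a defect in a stated procedure. This is not detail that could be left to a statistical analysis plan: the protocol sets out the method, and the method as set out has no random step and stops at 8 of 120 patients.

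On the natural reading, a fixed and printed block size of 8 makes 47.0% of assignments guessable against 25% by chance, with about 17 of 120 certain, provided that recruiters know past assignments and block starts.

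It would go too far to say that the trial is not randomised, or that its false-positive rate is 11%. Selection bias is a conditional risk, not a demonstrated one. It ranges from negligible under light steering to about 0.20 SD if every opportunity is used and the steered patients differ by 0.5 SD, and both of those inputs are assumptions. The correction should be made because the defect is clear and the remedy is cheap.

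**What to change.** Replace the paragraph with:

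> Patients are allocated 1:1:1:1 from a computer-generated list of permuted blocks, each block independently and randomly ordered, with randomly varying block sizes that are not disclosed to recruiters or printed in the protocol; each assignment is released only after eligibility and consent are recorded and the patient is irrevocably registered.

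Remove the reference to a single block and the phrase about numbering by order. The sizes must vary and stay undisclosed, because a smaller fixed size would not help: known blocks of 4 give (1/4 + 1/3 + 1/2 + 1) / 4 = 52.1% guessable, worse than the present 47.0%. The registration rule stops recruiters seeing the next arm. Only the varying, undisclosed sizes hinder guessing it from past assignments, and how far they do so depends on recruiters not inferring them.

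If patients are already enrolled, report the method actually used, and do not call the trial randomised if allocation was sequential. Separately, make the study design section's count of three groups agree with the four that it lists.

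The cost is a short script and someone outside recruitment to hold the list, using sealed envelopes or an existing data-capture module. The downside is that arm sizes may differ slightly if the last block is incomplete.
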